9.2. Events of Special Interest

9.2.1. Combined Elevations of Aminotransferases and Bilirubin

There is no clinically concerning signal of drug-induced liver injury associated with Edoxaban based on the extensive global Phase 3 experience involving over 34 048 Edoxaban subject-years exposure (with median drug exposure of ≈ 2.5 years among 18 010 Edoxaban treated subjects).

However, there will be ongoing monitoring of hepatic events with particular attention to combined elevations of aminotransferases and bilirubin (ALT or AST $> 3 \times$ ULN with simultaneous total bilirubin levels $> 2 \times$ ULN), without evidence of cholestasis (ALP $> 2 \times$ ULN is considered evidence of possible cholestasis) where no etiology for hepatocellular damage has been identified and a causal relationship to study drug cannot be ruled out.

Combined elevations of aminotransferases and bilirubin meeting the laboratory criteria of a potential Hy's Law case [ALT or AST $\geq 3 \times$ ULN with simultaneous total bilirubin levels $\geq 2 \times$ ULN] irrespective of whether they are serious or non-serious and whether causally related or not to study drug should always be reported to the Sponsor within 24 hours of the Investigator becoming aware of the event following the procedures outlined in Section 9.5.

In cases of liver laboratory abnormalities, or where there is evidence of liver dysfunction, it is important to ensure that the nature and the extent of liver injury is identified, and study subjects are monitored until the liver laboratory assessments return to normal.

If the subject discontinues study drug due to liver enzyme abnormalities, the subject will have additional clinical and laboratory evaluations which depending upon the clinical situation MAY include:

- Abdominal ultrasound;
- Hepatitis A, B, C, and E screening (anti-HAV IgM, HBsAg, anti-HCV plus viral titer, and evaluation for Hep E);
- Antinuclear antibody (ANA) and anti-SmAb;
- Cytomegalovirus (CMV);
- Epstein Barr virus (EBV);
- Additional evaluations as deemed appropriate by the Investigator to exclude other causes of liver enzyme and bilirubin elevations.

Subject's follow-up will be required until the values (transaminases, total bilirubin, and direct bilirubin) return to baseline. All clinically significant hepatic enzyme abnormalities and/or hepatic events must be documented in the eCRF. An adjudication dossier should be submitted for events that led to study drug discontinuation or were reported SAEs, where no alternative etiology has been found after work-up and where causal relationship to study drug cannot be ruled out.

The subject may re-start study medication if considered appropriate by the Investigator.

9.2.2. Reporting of Pregnancy/ Exposure in Utero

The Sponsor or designee must be notified of any subject that becomes pregnant while participating in a clinical study. All pregnancies must be followed to conclusion to determine their outcome. This information is important for both drug safety and public health concerns. It is the responsibility of the Investigator, or designee, to report any pregnancy in a subject, which occurs during the study.

Notification of the pregnancy should be submitted in the eCRF (AEs of special interest) within 24 hours and reported using Exposure in Utero Reporting form (paper form) and reported to the CRO medical monitor who will contact the Sponsor.

If the pregnancy is to be terminated, the anticipated date of termination should be provided. If the pregnancy ends for any reason before the anticipated date, the Investigator should notify the Sponsor. If the outcome of the pregnancy meets the criteria for immediate classification as an SAE (i.e., post-partum complications, spontaneous abortion, stillbirth, neonatal death, or congenital anomaly, including that in an aborted fetus), the Investigator should follow the procedures for reporting an SAE. At the completion of the pregnancy, the Investigator will document the outcome of the pregnancy in a follow-up Exposure in Utero Reporting Form.

9.3. Adverse Event

9.3.1. Definition of Adverse Event

Any untoward medical occurrence in a subject administered a pharmaceutical product and which does not necessarily have a causal relationship with this treatment. An AE can

therefore be any unfavorable and unintended sign (including an abnormal laboratory finding for example), symptom, or disease temporally associated with the use of a medicinal (investigational) product, whether or not considered related to the medicinal (investigational) product.

It is the responsibility of Investigators, based on their knowledge and experience, to determine those circumstances or abnormal laboratory findings which should be considered adverse events.

9.3.2. Unexpected Adverse Event

An unexpected AE is an AE, the nature or severity of which is not consistent with the reference safety information of any of the study medications or co-administered medications. The designation of expected or unexpected must be decided from the perspective of previously described AEs, not on the basis of what might be anticipated from pharmacological properties of a medicinal product. Determination of expectedness is the responsibility of Daiichi Sankyo and not the Investigator.

9.3.3. Expected Adverse Event

An expected AE is an event which is described in the reference safety information of the study drugs in nature, severity or incidence.

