MI	Myocardial infarction
mITT	Modified intention to treat
MLBCs	Major late bleeding complications
NACE	Net adverse clinical events
NSAID	Nonsteroidal anti-inflammatory drug
OAC	Oral anticoagulant(s)
OAP	Oral antiplatelet
PACT-Q	Perception of Anticoagulant Treatment Questionnaire
PCI	Percutaneous coronary intervention
P-gp	P-glycoprotein
PP	Per protocol
PT	Preferred Term
SAE	Serious Adverse Event
SAF	Safety analysis set
SAP	Statistical Analysis Plan
SAPT	Single antiplatelet therapy
SEE	Systemic embolic event
SmPC	Summary of product characteristics
SOP	Standard operating procedures
STS	Society of Thoracic Surgeons
SUSAR	Suspected Unexpected Serious Adverse Reaction
TAVI	Transcatheter aortic valve implantation
TEAE	Treatment-emergent adverse event
TEE	Transesophageal echocardiography or transesophageal echocardiogram
TEG	Thromboelastography
TIMI	Thrombolysis in Myocardial Infarction
TTE	Transthoracic echocardiography or transthoracic echocardiogram
ULN	Upper limit of normal
VKA	Vitamin K antagonist
WBCT	Whole blood clotting time
WHO	World Health Organization

DEFINITIONS SPECIFIC TO THIS PROTOCOL

Term	Definition for this protocol
Discontinuation	Permanent stoppage of study medication. The subject will not be allowed to restart study medication and should follow the transition procedures outlined in Section 5.2.1.1.2 or Section 5.2.1.2.2.
Interruption	A temporary stoppage of study medication. The subject is allowed to restart the study medication at the discretion of the Investigator.
End of TAVI	The clock for randomization starts with the removal of the sheath with hemostasis
End of Study	As an event driven study, enrollment will be stopped no later than at the attainment of a total of 320 subjects experiencing an adjudicated NACE across the combined treatment arms, and , the study will continue until the last subjects enrolled will have accomplished the minimum treatment duration of at least 6 months plus their Post-treatment Follow-up Visit. This Visit by the last subject enrolled will be defined as the end of the study (or common study end date [CSED]).
Major bleeding	Major bleeding is considered to include life-threatening and fatal bleeding.
Study drugs	Any study medication or prescribed oral antiplatelet (OAP) co-administered medication is defined within this protocol as a study drug.

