Study medication	The primary medications within this study are Edoxaban and VKA, referred to as study medications. The OAP co-administered medications (P12Y ₂ inhibitors or ASA) for the purpose of this protocol are NOT referred to as study medications; however, they are included within the term study drugs (see above).
Valve Thrombosis	Any thrombus attached to or near an implanted valve that occludes part of the blood flow path, interferes with valve function, or is sufficiently large to warrant treatment. Note that valve-associated thrombus identified at autopsy in a subject whose cause of death was not valve-related should not be reported as valve thrombosis.

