Daiichi Sankyo and/or CRO will inform Investigators, Institutional Review Boards (IRBs)/Ethics Committees (EtCs), and regulatory authorities of any suspected unexpected serious adverse reactions (SUSARs) occurring in other study centers or other studies of the investigational drug, as appropriate per local reporting requirements. Daiichi Sankyo and/or CRO will comply with any additional local safety reporting requirements. Detailed SAE processing, distribution and reporting will be laid out in sponsors SAE Flow Plan.

In the US, upon receipt of the Sponsor's notification of SUSARs that occurred with the study drug, unless delegated to the Sponsor, it is the Investigator's responsibility to inform the IRB/EtC per Sponsor's instruction.

In the European Economic Area (EEA) states, it is the Sponsor's responsibility to report SUSARs to all ECs.

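### Sections 9.3.2 and 9.3.3 are not complements and test expectedness against the pooled safety information of all study drugs, so a serious reaction new for edoxaban but described for another study drug can fall outside SUSAR notification

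*Combined protocol and SAP*

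**What the plan says.** Section 9.3.2 makes an adverse event unexpected when it is one "the nature or severity of which is not consistent with the reference safety information of any of the study medications or co-administered medications". It assigns the determination to the sponsor "and not the Investigator". Section 9.3.3 makes an event expected when it is "described in the reference safety information of the study drugs in nature, severity or incidence".

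The protocol's table of definitions fixes the terms. On study drugs it says: "Any study medication or prescribed oral antiplatelet (OAP) co-administered medication is defined within this protocol as a study drug". On study medication it says: "The primary medications within this study are Edoxaban and VKA, referred to as study medications". Study drugs in 9.3.3 therefore covers the anticoagulants of both arms and the antiplatelets.

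Section 9.7 commits the sponsor or CRO to inform investigators, ethics committees and authorities of "any suspected unexpected serious adverse reactions (SUSARs) occurring in other study centers or other studies of the investigational drug". It leaves detail to another document, which is not among those supplied: "Detailed SAE processing, distribution and reporting will be laid out in sponsors SAE Flow Plan".

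Section 9.6 takes serious stroke, TIA, systemic embolism, MI and bleeding out of expedited reporting, whatever their expectedness, and has the DSMB review them unblinded.

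**The concern.** Two things look wrong. First, a pair of definitions that should divide all events into two classes does not do so: one uses *or* for failing the test, and the other uses *or* for passing it. Second, neither section ties the judgement to the drug suspected of causing the event. A subject on edoxaban takes no study VKA, and under Section 3.1 may take no antiplatelet at all, yet the safety information of those drugs can count towards calling an edoxaban reaction expected.

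Expectedness decides whether a suspected serious reaction is notified under 9.7. Because 9.6 already removes the main thrombotic and bleeding events from expedited reporting, this classification controls the serious suspected reactions that remain, such as hepatic or hypersensitivity reactions. Section 1.3 acknowledges that edoxaban's risks after TAVI are unknown, so a test specific to edoxaban has a purpose in this trial.

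**Working it through.** No arithmetic applies. The check sets the definitions side by side and runs types of event through them.

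**Logic of the two tests.** Let N and S mean that the event is consistent with the RSI in nature and in severity, and let I mean that its incidence is as described.

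- 9.3.2: unexpected = (not N) or (not S). Its complement is N and S.
- 9.3.3, read literally: expected = N or S or I.

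These are not complements. They disagree whenever N or S fails and at least one of N, S and I holds. Incidence appears only in 9.3.3.

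**Which RSI.** 9.3.3 refers to the study drugs, which by definition pools edoxaban, VKA and the antiplatelets. 9.3.2 refers to any of the study and co-administered medications. This can be read in two ways:

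- *Pooled*: the event is consistent with none of the RSIs. This is the more natural reading.
- *Any one*: the event is inconsistent with at least one RSI. A reaction fully described for edoxaban but absent from clopidogrel's RSI would then be unexpected, which moves 9.3.2 further from 9.3.3.

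**A serious event suspected to be caused by edoxaban:**

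| Type of event | 9.3.2, pooled reading | 9.3.3, literal reading | Result |
|---|---|---|---|
| Listed for edoxaban, severity as described | Not unexpected | Expected | Sections agree |
| Listed for edoxaban by nature, more severe than described | Unexpected, unless another study drug's RSI covers that severity | Expected | Sections conflict |
| Absent from edoxaban's RSI, described for VKA, clopidogrel or ASA | Not unexpected | Expected | Outside SUSAR notification under both |
| In no study drug's RSI | Unexpected | Not expected, since nothing describes it | Sections agree; remains a SUSAR |

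An event of listed nature and severity that is more frequent than described shows the mismatch over incidence. 9.3.2 does not make it unexpected. 9.3.3 makes it expected on the literal reading, but would not if all three features had to match.

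**What resolves the conflict.** No section says which definition governs, names the RSI document for each drug, or limits the comparison to the suspected drug.

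**The case against.** The strongest reply is that 9.7 is triggered by the term unexpected, which 9.3.2 defines, so 9.3.2 governs in practice. On that view a listed edoxaban reaction of greater severity is notified, unless pooling intervenes. This stands. The severity case is a conflict between sections, and the section that defines the trigger routes it correctly. A reader might infer that more severe edoxaban reactions will generally go unexpedited; that follows only if 9.3.3 is applied instead.

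It can also be said that the literal reading of 9.3.3 is uncharitable, since it would make an event expected on a match in incidence alone. That suggests loose drafting. The text still offers no other rule, and those who classify events have to work from it.

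On pooling, 9.3.2 has the second reading shown above, and the causality section (9.3.6) and 9.7 speak of the study drug or the investigational drug in the singular, which hints at drug-specific assessment. But study drug is itself the pooled defined term, 9.3.6 concerns causality and not expectedness, and 9.3.3 pools on any reading.

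Finally, other safeguards exist. SAEs are reported within 24 hours (9.6), as are combined liver elevations whatever their cause (9.2.1); fatal SAEs enter the global safety database (9.6); and local reporting requirements and the regulations listed in Section 15.1 apply. These keep events visible to the sponsor, and the SAE Flow Plan may contain a correct rule. None of them corrects the definitions that decide onward notification.

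**Conclusion.** The point holds, within limits. The two sections do not form complementary definitions, and as written they allow a serious suspected edoxaban reaction that is absent from edoxaban's RSI, but described for VKA or an antiplatelet, to be classed as expected and left out of SUSAR notification. This rests on the pooled wording of 9.3.3 and the more natural reading of 9.3.2.

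Three stronger conclusions are not supported:

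- A reader might infer that any new edoxaban reaction could be missed. An event in no study drug's RSI is unexpected under 9.3.2 and not expected under 9.3.3.
- A reader might count two of the four types in the table as misrouted and treat that as a measure. The types carry no frequencies; one is a conflict between sections and only one is outside notification under both.
- A reader might infer that events will in fact go unreported. The SAE Flow Plan was not supplied, so the documents show only that the protocol permits it.

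The size in events cannot be derived. The reach is serious suspected reactions outside the endpoint events exempted by 9.6. The primary analysis, the target of 320 events and the type I error are unaffected. This is an inconsistency in safety-reporting wording that should be corrected.

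**What to change.** Rewrite 9.3.2 and 9.3.3 as exact complements:

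- Judge expectedness separately for each drug suspected of causing the event, against that drug's own RSI, and name the RSI document for each drug.
- Class the event as expected only if both its nature and its severity are consistent with that RSI, and as unexpected otherwise.
- Delete incidence from 9.3.3, and delete the pooling over study and co-administered drugs from both sections.
- Align the SAE Flow Plan with the new wording.

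The cost is an edit to two short sections and one operational document, and possibly a few more expedited reports. No treatment rule, endpoint or analysis changes.

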9.3.4. Serious Adverse Event

A serious adverse event is any untoward medical occurrence that at any dose:

- Results in death
- Is life-threatening
- Requires inpatient hospitalization or prolongation of existing hospitalization
- Results in persistent or significant disability/incapacity
- Is a congenital anomaly/birth defect, or
- Is an important medical event.

Note: The term “life-threatening” in the definition of “serious” refers to an event in which the subject was at risk of death at the time of the event; it does not refer to an event which hypothetically might have caused death if it were more severe (International Council on Harmonisation [ICH] E2A Guideline. Clinical Safety Data Management: Definitions and Standards for Expedited Reporting, Oct 1994).

Medical and scientific judgment should be exercised in deciding whether expedited reporting is appropriate in other situations, such as important medical events that may not be immediately life-threatening or result in death or hospitalization but may jeopardize the subject or may require intervention to prevent one of the other outcomes listed in the definition above. Examples include allergic bronchospasm, convulsions, and blood dyscrasia or development of drug dependency or drug abuse.

Notes:

- Procedures are not AEs or SAEs, but the reason for the procedure may be an AE or SAE.
- Pre-planned (prior to signing the Informed Consent Form) procedures or treatments requiring hospitalizations for pre-existing conditions that do not worsen in severity are not SAEs.

9.3.5. Severity Assessment

The following definitions should be used to assess intensity of adverse events:

- Mild: Awareness of sign or symptom, but easily tolerated, i.e., does not interfere with subject's usual function.
- Moderate: Discomfort enough to cause interference with usual activity.
- Severe: Incapacitating with inability to work or do usual activity, i.e., interferes significantly with subject's usual function.

Severity vs. Seriousness: Severity is used to describe the intensity of a specific event whereas the event itself; however, may be of relatively minor medical significance (such as severe headache). This is not the same as "seriousness," which is based on subject/event outcome at the time of the event.

9.3.6. Causality Assessment

The Investigator should assess causal relationship between an adverse event and the study drug on the basis of his/her clinical judgment and the following definitions. The causality assessment must be made based on the available information and can be updated as new information becomes available.

- 1 = Related:
 - The AE follows a reasonable temporal sequence from study drug administration, and cannot be reasonably explained by the subject's clinical state or other factors (e.g., disease under study, concurrent diseases, and concomitant medications).
 - or
 - The AE follows a reasonable temporal sequence from study drug administration, and is a known reaction to the drug under study or its chemical group, or is predicted by known pharmacology.
- 2 = Not Related:
 - The AE does not follow a reasonable sequence from study drug administration, or can be reasonably explained by the subject's clinical state or other factors (e.g., disease under study, concurrent diseases, and concomitant medications).

9.3.7. Action Taken Regarding Study Drug(s)

- 1 = Dose Not Changed: No change in study drug dosage was made.

- 2 = Drug Withdrawn: The study drug was permanently stopped.
- 3 = Dose Reduced: The dosage of study drug was reduced.
- 4 = Drug Interrupted: The study drug was stopped for a period of time.
- 5 = Dose Increased: The dosage of study drug was increased.
- Not Applicable: (e.g., Subject died, study treatment had been completed prior to reaction/event, or reaction/event occurred prior to start of treatment)

9.3.8. Other Action Taken for Event

- 1 = None: No treatment was required.
- 2 = Concomitant medication required: Prescription and/or over-the-counter medication were required to treat the adverse event.
- 3 = Concomitant medication permanently discontinued: Prescription and/or over-the-counter medication other than the assigned anticoagulant-based regimen was permanently discontinued due to the adverse event.
- 4 = Concomitant medication temporarily interrupted: Prescription and/or over-the-counter medication other than the assigned anticoagulant-based regimen was temporarily interrupted due to the adverse event.
- 5 = Other.

9.3.9. Adverse Event Outcome

- 1 = Recovered/Resolved: The subject fully recovered from the adverse event with no residual effect observed.
- 2 = Recovered/Resolved with Sequelae: The residual effects of the adverse event are still present and observable. Include sequelae/residual effects.
- 3 = Not Recovered/Not Resolved: The adverse event itself is still present and observable.
- 4 = Fatal
- 5 = Unknown

The Investigator should follow subjects with AEs until the event has resolved or the condition has stabilized. In case of unresolved adverse events including significant abnormal laboratory values at the end of study assessment, these events will be followed up until resolution or until they become clinically not relevant.

9.4. Timing of Adverse Event Reporting

All AEs must be recorded and reported from the stated starting point of the clinical trial (immediately after signing ICF) including AEs taking place during the administration of other drugs. Even if the subject has not yet received the investigational treatment, untoward medical occurrences have to be treated as AEs.

The period of AE reporting is defined as follows:

AEs that occur within 30 days after the last dose of the assigned study treatment, which are reported to the Investigator (regardless of the date of a Follow-up Visit) must be recorded in the eCRF.

9.5. Reporting SAEs/AEs

9.5.1. Documentation

To effectively evaluate the safety profile of the study treatments, this study will report all (S)AEs occurring after the subject signs the IC and as long as the subject remains in the study or until the study is terminated by the Sponsor (i.e., the end of the study), whether observed by the Investigator or reported by the subject. All AEs will be recorded on the AE/Outcome eCRF page(s) and include:

- Any components of the study endpoint assessments (see Section 7);
- AEs that meet seriousness criteria (see Section 9.3.4);
- AEs that result in interruption or discontinuation of the assigned study treatment;
- Any other AE.

All laboratory results and vital signs should be evaluated by the Investigator regarding clinical significance. Isolated abnormal laboratory results or vital sign findings that are not part of a diagnosis should be reported as AEs or SAEs. Medical conditions (including laboratory values/vital signs that are out of range) that were diagnosed or known to exist prior to IC will be recorded as part of medical history.

All SAEs are to be reported as long as the subject remains in the study or until the study is terminated by the Sponsor (i.e., the end of the study) and according to the procedures in Section 9.6. Always report the diagnosis as the AE or SAE term. When a diagnosis is unavailable, report the primary sign or symptom as the AE or SAE term with additional details included in the narrative until the diagnosis becomes available. If the signs and symptoms are distinct and do not suggest a common diagnosis, report them as individual entries of AE or SAE. For events that are serious due to hospitalization, the reason for hospitalization must be reported as the SAE (diagnosis or symptom requiring hospitalization).

AEs may be directly observed, reported spontaneously by the subject or by questioning the subject at each study visit. Subjects should be questioned in a general way, without asking about the occurrence of any specific symptoms. The Investigator must assess all AEs to determine seriousness, severity, and causality, in accordance with the definitions in Section 9.3.5 and Section 9.3.6. The Investigator's assessment must be clearly documented in the site's source documentation with the Investigator's signature.

